4.3. Statistical Methods for Primary Efficacy Analysis

Primary efficacy analysis will include the modified intention to treat sample as defined in section 3.3 above.

The primary hypothesis can be stated as follows.

Under the null hypothesis: The 1-year event rate is 15% and the two treatment groups do not differ in their time to event hazard rates.

Under the alternative hypothesis: The 1-year event rate is 9.45% for patients treated with lithium and 15% for patients in the placebo group, resulting in an absolute reduction from 15% to 9.45% = 5.55% and a relative reduction of $(15 - 9.45)/15 = 37\%$. The group on lithium augmentation has a lower hazard rate than the placebo augmentation group with a hazard ratio for lithium therapy compared to control therapy lower than or equal to 0.61.

We will test this hypothesis with a two sided log rank test at 90% power and 4.8% Type I error (i.e., 5% overall error allows for one interim test at 0.2%). Null hypothesis will be rejected if the hazard ratio exceeds $1/0.61 = 1.64$ or falls below 0.61.

A significant difference showing that the lithium augmentation compared to placebo decreases the hazard of suicidal self-violence will be regarded as a positive result, whereas a result that shows lithium augmentation does not significantly differ from placebo or significantly increases the hazard rate relative to placebo will be regarded as a negative result.

Log rank test will be followed by Cox proportional hazards regression modeling to provide the hazard rates, their ratio and the 95% confidence interval about the ratio.

We will test the proportional hazards assumption by including a time*treatment interaction term in the model and use graphic methods to study goodness of fit as described in Anderson et. al., 1991.

The SAS code for the primary analysis is as follows, where, tx is coded as {1=lithium, 0=placebo}, event is coded as {1=adjudicated outcome, 0=otherwise}, and FUdays is counting number of days from randomization date to the first occurrence of (adjudicated outcome, death, 12 month date, or last study visit/contact date).

Log-Rank Test:

```
title "Survival Estimates by Month";
proc lifetest data=endpt plots=(s); time FUdays*event(0); strata tx; run;
quit;
proc lifetest data=endpt method=life plots=(ls) intervals=30 90 120 150
180 210 240 270 300 330 365; time FUdays*event(0); strata tx; run; quit;

title "Survival Estimates by Month";

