8.3.5. Section D: Safety Assessment (CLOSED SESSION ONLY)

Table D1. Rates of Non-Serious Related Adverse Events (NAEs), by Site and Treatment
Table D2. Rates of Serious Adverse Events (SAEs), by Site and Treatment
Table D3. **Reported in OPEN SESSION only**
Table D4. Summary of Serious Adverse Events (Form B15), by Treatment
Table D5. Related Non-Serious Adverse Events by System Organ Class, by Treatment
Table D6. Serious Adverse Events by System Organ Class, by Treatment
Table D7. Deaths Reported, by Treatment

9. Analytic Tables not included in the Data Monitoring Committee Reports

Following analytic tables will be generated annually and made available to the study team, Upon request of the DMC at the initial meeting these tables will not be included in the DMC report.

Table X1. Military Service

Table X2. Medical and Psychiatric History

Table X3. MINI Module Assessment

Table X4. Baseline Physical Assessments

Table X5. Baseline Laboratory Results

Table X6. Baseline Psychiatric Measures

Table X7. Baseline Substance Use (SCID-SUD)

Table X8. Concomitant Medications

10. Sample Size and Power

CSP590 is targeted to enroll a total of 1862 subjects, and approximately 40% of the enrolled sample is expected to terminate early (i.e., 20% complete data loss), thereby resulting in an analytic sample of 1490 evaluable subjects. With the evaluable study sample equally allocated to the 2 treatment arms, the study is powered to detect at least a 37% reduction in the one year outcome event rate.

Expected event rates used in sample size estimation to achieve 90% statistical power for hypothesis testing were 15% re-attempt rate in the placebo group and 9.45% re-attempt rate in the lithium group. Justification for selecting these rates to estimate sample size and power are provided in the protocol.

The results for the primary outcome measure will be analyzed by a two-sided log-rank test to detect either a hazards ratio that exceeds $1/0.61=1.64$ or is less than 0.61, i.e., the test has 90% power to detect a hazard ratio of 1.64 or larger or 0.61 or less.

These estimations are adjusted for an O'Brien-Fleming stopping rule with one interim and one final test of hypothesis, and allow for an overall two-sided type I error of 5% for the hypothesis being tested. Hence, the interim primary hypothesis will be tested at $p=0.002$ level (allowing for 0.2% Type I error), and the final primary hypothesis will be tested at $p=0.048$ level (allowing for 4.8% Type I error).

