Tables 2 below consider three scenarios for possible shift in statistical power, specifically (a) in the event that an intervention effect different from the projected 37% reduction is observed, (b) in the event that the sample size for the study falls either above or below the targeted 1490 evaluable subject mark, and (c) in the event that the event rate is below the expected 15% in the placebo group. This study will have greater than 80% statistical power at 5% overall error if the observed effect is as low as 33% reduction, if the final evaluable sample is as low as 1200 subjects, or if we observe an event rate as low as 12% in the placebo group.

Table 2: Evaluation of variability in Statistical Power assuming 5% Overall Type I error.

(a) Change in statistical power for fixed sample size and a range of effect sizes

		Event Rates				
Evaluable N	N per arm	Placebo	Active	#Events	Effect	Power
1490	745	15%	11%	190	30%	73%
1490	745	15%	10%	188	31%	77%
1490	745	15%	10%	187	33%	81%
1490	745	15%	10%	185	35%	85%
*1490	745	15%	9.5%	182	37%	90%
1490	745	15%	9%	179	40%	94%

(b) Change in statistical power for fixed effect size and a range of sample sizes

		Event Rates				
Effect	Placebo	Active	Evaluable N	N per arm	#Events	Power
37%	15%	9.5%	1700	850	208	93%
*37%	15%	9.5%	1490	745	182	90%
37%	15%	9.5%	1400	700	171	88%
37%	15%	9.5%	1200	600	147	83%
37%	15%	9.5%	1100	550	134	79%
37%	15%	9.5%	1000	500	122	75%

(c) Change in statistical power for fixed effect and sample size and a range of event rates

Total N	N per arm	Event Rates		#Events	Effect	Power
		Placebo	Active			
*1490	745	15%	9.5%	182	37%	90%
1490	745	14%	8.8%	170	37%	88%
1490	745	13%	8.2%	158	37%	85%
1490	745	12%	7.6%	146	37%	82%
1490	745	11%	6.9%	134	37%	78%
1490	745	10%	6.3%	121	37%	73%

*Highlight indicates parameters proposed in CSP590

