10.1. Interim Analysis

We will conduct one interim analysis after half of the participants have completed their 12 month follow up. This analysis is projected to take place approximately 2.5 years after initiation of enrollment (assuming it will take 1.5 years to enroll half the sample and allow 12 months of follow-up). After adjusting for attrition, a sample of 746 evaluable subjects, (373 in each group), is expected to be included in the analysis.

Projecting the same event rate in this sub-sample we expect to observe a 15% or 112 events (56 events in each group) under the interim null hypothesis that event rates are equal in the treatment groups. Under the interim alternative hypothesis, the absolute reduction from 15% to 5.3% is $(15-5.3) = 9.7\%$, the relative reduction is $(15-5.3)/15 = 65\%$, and the hazard ratio (treatment hazard rate/control hazard rate) is 0.34. The interim log-rank test is two-sided, and the interim null hypothesis will be rejected if the hazard ratio exceeds $1/0.34 = 2.94$ or falls below 0.34. Using the O'Brien-Fleming procedure, (Turnbull & Jennison, 2000), this analysis will have a Type I error of 0.2%.

We will confer with the Data Monitoring Committee members and the program leadership for potential stopping guidelines based on results from interim efficacy analysis.

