10.2. Futility Analysis

As a part of the interim futility analysis we will estimate the conditional probability (CP) of observing a significant final result based on assumptions about the distribution of future event rates. Assumptions for additional data to be collected in the second half of the study are:

- (1) “no-change” scenario where future event rates will occur at the same rate as currently observed rates,
- (2) “expected” scenario where future event rates occur at the rates expected at the beginning of the trial (i.e., as proposed in the protocol),
- (3) “extreme” scenario where future event rates occur at the currently observed overall event rate, but all new events occur in the placebo group so as to set the best scenario for achieving a significant difference.

For conditional probability estimation, we will use the estimation method developed by Proschan, Lan, and Wittes, 2006 and further described by Jitlal et. al, 2012, where

CP at a specific time = $1 - \Phi[(Z\alpha/2 - E[B(1)|B(t)])/\sqrt{1-t}]$,

$E[B(1)|B(t)]$ is the expected value of $B(t)$ at the end of the trial (when $t=1$), given the data observed until point t .

The information fraction, t , is the number of observed events so far, expressed as a proportion of the planned number of events.

11. Final Statistical Report

The final statistical report for CSP590 will be the submitted and accepted primary manuscript which includes results from the primary ITT analysis as outlined in section 4 and any additional analyses to be conducted based on the journal's peer review process. At minimum, the final statistical report will include the CONSORT diagram (section 8.3.1), descriptive characteristics of the ITT cohort (section 8.3.2), medical and psychiatric history of the cohort (section 9), and the primary analysis results (section 4.3).

12. References

- MacKinnon, D. P.; Lockwood, C. M. Hoffman, J. M., West S. G., Sheets V. A Comparison of Methods to Test Mediation and Other Intervening Variable Effects. *Psychological Methods* 7: 83–104, 2002

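### The SAP's futility calculation uses one fixed planned event count as the information denominator in a trial sized by patients and time, so conditional power is off whenever the event total departs from about 182

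*SAP*

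**What the plan says.** SAP 10.2 plans a conditional power calculation at the single interim look and defines its time scale: "The information fraction, t , is the number of observed events so far, expressed as a proportion of the planned number of events". No number is attached to the planned events there. The nearest design figure is the starred row of SAP Table 2(a) ("15% 9.5% 182 37% 90"), which gives 182 events for 1490 evaluable patients under the assumed "15% re-attempt rate in the placebo group and 9.45% re-attempt rate in the lithium group".

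Three scenarios are set for the second half of the trial: future events at the rates seen so far (no-change), future events at the design rates (expected), and an extreme case in which "all new events occur in the placebo group so as to set the best scenario for achieving a significant difference".

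Both the look and the end of the trial are fixed by patients and follow-up. SAP Section 2 follows each participant for 12 months. SAP 10.1 places the look after half of the participants have completed that follow-up, with 746 evaluable, and says that "we expect to observe a 15% or 112 events (56 events in each group) under the interim null hypothesis". SAP 4.3 states the null in the same terms: "Under the null hypothesis: The 1-year event rate is 15% and the two treatment groups do not differ".

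**The concern.** Conditional power depends on how much information is still to come. In an event-driven trial the planned event count is the final information, so observed over planned is the right fraction. This trial is not event-driven. Its final event count is whatever the enrolled patients produce in 12 months, and 182 is only the count expected if lithium works as designed.

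The SAP's own interim null shows the conflict. It expects 112 events from half the patients, which points to about 224 at the end, yet the rule treats 112 as 112/182 of the total. The scenarios add to this, because each projects future event rates while t does not change with them.

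The stake is the figure that the Data Monitoring Committee (DMC) reads at the only planned look. The protocol (Section XVII, Premature Termination of the Study) lists an interim trend that is unlikely to change as a possible ground for stopping.

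**Working it through.** **Inputs.** 745 evaluable per arm, 15% v 9.45% (SAP Section 10). 746 evaluable at the look (SAP 10.1). Final two-sided level 0.048 (SAP 4.3: "We will test this hypothesis with a two sided log rank test at 90% power and 4.8% Type I error"), so the critical value is 1.977.

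**The plan's own figures reproduce.**
- Events: 745 × (0.15 + 0.0945) = 182.2.
- Hazard ratio: ln(1 − 0.0945)/ln(1 − 0.15) = 0.611.
- Power with 182 events at level 0.048: 90.0% (Freedman) or 91.1% (Schoenfeld), in line with the stated 90%.
- Interim null: 746 × 0.15 = 111.9, or 112 events.

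**Information fraction on the SAP's null (15% in both arms).**
- SAP rule, taking 182 as planned: t = 112/182 = 0.615.
- No-change: the final total is 1490 × 0.15 = 223.5, so t = 112/223.5 = 0.50.
- Expected: the remaining 744 patients yield 744 × (0.15 + 0.0945)/2 = 91 events, so t = 112/(112 + 91) = 0.55.

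**Conditional power.** The SAP formula is CP = 1 − Φ[(1.977 − E)/√(1 − t)], with E = Z√t + (1 − t)θ. The drift θ is Z/√t for no-change and ½·|ln 0.611|·√D for expected, where D is the final event total.

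Expected scenario, 112 events, Z = 0:
- SAP: D = 182, θ = 3.325, E = 0.385 × 3.325 = 1.279. CP = 1 − Φ(0.698/0.620) = 13%.
- Scenario-consistent: D = 203, θ = 3.512, E = 0.448 × 3.512 = 1.574. CP = 1 − Φ(0.403/0.670) = 27%. A log-rank simulation of this case (4,000 runs) also gave 27%.

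No-change scenario, 112 events, Z = 1:
- SAP: E = 1/√0.615 = 1.275. CP = 1 − Φ(0.702/0.620) = 13%.
- Scenario-consistent: E = 1/√0.50 = 1.414. CP = 1 − Φ(0.563/0.707) = 21%.

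| Rate in both arms (events at look) | Scenario, Z | SAP rule | Scenario-consistent |
|---|---|---|---|
| 15% (112) | expected, 0 | 13% | 27% |
| 15% (112) | expected, 0.5 | 31% | 48% |
| 15% (112) | no-change, 0 | 0.1% | 0.3% |
| 15% (112) | no-change, 1 | 13% | 21% |
| 10% (75) | expected, 0 | 49% | 37% |
| 10% (75) | no-change, 1 | 29% | 21% |

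**Where the error changes sign.** The rule is exact when the final total is 182, that is, at a pooled rate of 182/1490 = 12.2%. At the design alternative the look has 91 events and t = 91/182 = 0.50, with no error.

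**Where the formula fails.** If only completers count, t reaches 1 at 182/746 = 24.4%. That rate is an assumption, above the 12% to 18% that the protocol draws from earlier trials (Section VII). The SAP does not say whether patients with partial follow-up at the look are counted. If they are, and accrual is uniform (assumption), about two thirds of final events are in hand, and t reaches 1 at 182/(1490 × 2/3) = 18.3%.

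**The case against.** Five points can be made for the plan.

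1. *The rule is accurate where a wrong stop would matter most.* Across SAP Table 2(a), effects of 30% to 40% give 179 to 190 events, so t at half the total is 0.49 to 0.52. Across Table 2(c), placebo rates of 10% to 15% give 121 to 182 events, so t is 0.33 to 0.50 and conditional power is correct or too high. This stands. A reader might infer that the rule understates conditional power whenever lithium has no effect, and so pushes towards a wrong futility stop. The documents do not support that. The sign depends on the pooled event rate, not on the absence of effect, and the protocol (Section VIII, Repeat rates) says that the direction of any shift in the rate cannot be estimated. At 15% in both arms there is no benefit to miss.

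2. *182 is inferred.* This stands. One could instead take about 224 from SAP 10.1, which makes t = 0.50 under the null. At the design alternative t would then be 91/224 = 0.41 instead of 0.50, so a different fixed number moves the problem without removing it.

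3. *No decision rule is affected.* The protocol (Section XIX, Monitoring) offers conditional power to the DMC at its request, and the SAP sets no threshold. This stands and limits the severity.

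4. *The final level is already stated as 0.048.* This stands. Writing 1.977 into SAP 10.2 only makes it explicit.

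5. *The extreme scenario is meant as a best case.* This stands. It says little: 67 lithium and 45 placebo events at the look plus 70 placebo-only events gives Z = (45 + 70 − 67)/√182 = 3.6. A reader might conclude that it must be removed, but the SAP presents it as a bound, so removal is a matter of preference.

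**Conclusion.** The point holds as an inconsistency between a fixed event denominator and a design whose final information is set by patients and follow-up. Followed as written, with 182 as the planned count, the rule gives the DMC a conditional power that is too low above a pooled rate of about 12.2% and too high below it. At the rates the documents consider, the expected scenario moves by 10 to 20 points (at 15%, 14 points at Z = 0 and 17 at Z = 0.5; at 10%, 12 points the other way at Z = 0). The no-change scenario moves by about 8 points at Z = 1 and immaterially at Z = 0.

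These figures assume that 182 is the intended denominator, that only completers count at the look, and that the interim sample is the 746 in the SAP. A reader might infer a threat to type I error or to the primary analysis. There is none, because the effect stops at an advisory figure. The rating is should-fix.

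**What to change.** In SAP 10.2, replace the single denominator. For each scenario, set t = observed events / (observed events + future events projected under that scenario from remaining patient follow-up, including patients still to be enrolled), and use the same projected total in the drift. Report the projected total beside each conditional power. State whether patients with partial follow-up at the look contribute events and, if they do, project only their remaining time. Name the critical value for the final level of 0.048 (1.977). Keep the extreme scenario if wished, labelled as an upper bound only.

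The cost is a paragraph of SAP text and a few lines of code, settled before the interim data are seen. Sample size, the efficacy boundary and the primary analysis do not change.
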